### Exclusion criteria

(a) Any physical or mental condition or disorder, which, in the opinion of the investigator, may affect participation in the study.

### A4.1.3 Recruitment

Potential participants will be provided with a copy of the Participant Information Sheet (PIS) by the Service Provider at their pre-assessment visit. The PIS will provide detailed information about the rationale, design and personal implications of the study, as well as contact details of the central study team. Patients will be invited to call the team if they have any questions or concerns about the study, or if they would like to register their interest in taking part. Once a participant has confirmed their interest in the study, the central research team will then liaise with the local research site to organise the first study visit.

### A4.1.4 Informed consent

In all instances, potential participants will be given as long as they need, ideally at least 24 hours, to consider participation and will be given the opportunity to discuss the study with their family and healthcare professionals before being invited to give consent to participate in the study.

Assenting participants will then be formally assessed for eligibility by the PI or authorised delegate as listed on the trial specific delegation log and invited to provide informed, written consent. The right of the patient to refuse consent without giving reasons will be respected. A copy of the consent will be given to the participant, and one filed in the Study Files. The written consent will be taken by the PI or authorised delegate, who has signed / dated the staff authorisation / delegation log.

### A4.1.4.1 Participants who withdraw consent

Participants are free to withdraw from the study at any time for any reason without prejudicing any further treatment and with no obligation to give the reason for withdrawal.

In the case of a participant withdrawal, data collected up until the point of withdrawal will be retained for the full archive period in line with the Data Protection Act 2018. Samples and data collected from samples cannot be withdrawn once they have been used.

### A4.1.4.2 Managing/replacing participants who withdraw early

Participants who withdraw from the study early will not be replaced.

A4.1.5 Methods of assessment

### A4.1.5.1 Participant Reported Outcomes

Participants will be asked to complete three additional questionnaires at the baseline and 6 month visits:

(a) Knee injury and Osteoarthritis Outcome Score (KOOS) and / or Hip disability and Osteoarthritis Outcome Score (HOOS)

These questionnaires assess the participant's opinion of their knee/hip. Questions are asked regarding knee/hip symptoms, pain, function in daily living and function in sports and recreational activities. Each question is assigned a score from 0-4. Total scores can range from 0 (most extreme symptoms) to 100 (no symptoms). Participants will complete one or both dependent on whether they have knee OA, hip OA, or both.

### (b) Adapted Nordic questionnaire (Kuorinka et al., 1987)

A standardised questionnaire designed to answer the following question: "Do musculoskeletal troubles occur in a given population, and if so, in what parts of the body are they localised?" The questionnaire includes a shaded manikin highlighting regions of the body and asks the participant to indicate which regions they experience trouble (ache, pain or discomfort). For the purposes of this study, the questionnaire has been adapted to determine if the pain is new onset post-COVID-19 and to rate the overall (average) severity of the pain in the past week on a 0-10 numerical rating scale (NRS), where 0 is no pain and 10 is pain as bad as it can be.

### (c) Musculoskeletal Health Questionnaire

The Musculoskeletal Health Questionnaire MSK-HQ is a short questionnaire that allows people with musculoskeletal conditions (such as arthritis or back pain) to report their symptoms and quality of life in a standardised way. It contains 14 questions scored on a 5 point scale from 'not at all' to 'very severe', with an additional question about physical activity levels in the last week.

### A4.1.5.2 Biological samples

A maximum of 9 mls of blood will be taken at each study visit to enable measurement of inflammatory biomarkers, including hsCRP and IL-6.

The blood will be drawn into 1 x 9ml clot tube. For further information on sample collection and processing, see the latest version of the Biological Sample Collection Form.

As part of the biological sub study personal details will be removed from all research blood samples after separation into the component parts and before testing, samples will be identifiable by subject identification number only. It will be possible to link the study and laboratory databases through this unique number so that long-term disease outcomes and predictors of response to future treatments can be examined. Biological samples will be stored at recruitment sites and the LBU Laboratory for the duration of the study with explicit consent for the samples to be stored beyond the duration of the study for future research. Any samples that are not used at the end of this study will be transferred to an HTA-approved Research Tissue Repository

once the project specific approval expires and will be used in future studies within this research remit. Aliquots of these biologic materials may be shared for research purposes only with national and international academic and industrial collaborators worldwide. The samples will be fully anonymised of patient identifiers before transportation.

Contextual data may also be included in any submissions. Access to such non-identifiable data will be reviewed for appropriateness before release. The transport of samples will be via IATA certified staff, logged and registered via a database and sent in a clinical fashion via independent internal transport.

### A4.1.5.3 Data Linkage

We will ask patients for their permission to link their data to the LCD minimum dataset via their unique referral ID, so the inflammatory data can be linked to the LCD clinical data.

### A4.1.6 Study procedures by visit

Summary schedule of study assessments

| STUDY VISIT  | Pre-baseline | Visit 1
Baseline* | Visit 2
6 month follow-
up
(+/- 4 weeks) |
|--|--------------|----------------------|---|
| Study information provided to potential participants in clinic | х            |                      |   |
| Informed consent   |              | Х                    |   |
| Inclusion / Exclusion  |              | Х                    |   |
| Participant questionnaires                                     |              | Х                    | Х   |
| Biological sample  |              | Х                    | Х   |

\*As close to commencement of the LCD programme as possible

^To coincide with completion of the food re-introduction phase

A4.1.7 Data handling

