
Following receipt of ethical approval, we will ask each service provider to send the Participant Information Sheet (PIS) (complete with their unique referral ID) which includes a link to the survey and freephone number to complete the survey over the phone, at the following time points:

- Baseline survey to be completed between the initial assessment and the first week of the TDR phase.
- End of TDR survey to be completed at during the last week of the TDR phase and first week of the food reintroduction phase.
- End of food reintroduction survey to be completed during the last week of the food reintroduction phase and first week of the maintenance phase.
- Maintenance phase to be completed during the last two weeks of the maintenance phase.
- Withdrawal survey to be sent to all participants at the point of withdrawal.

<sup>4 PowerPoint Presentation (sportengland.org)

<sup>5 Security Statement // Qualtrics

A freephone number will be established for patients who would rather complete the survey verbally or in another language, to enable participation irrespective of literacy, language, visual ability or internet access (call handlers (with assistance of a translator where required) will complete the online survey on behalf of the participant). We will work with the PPI group to develop a short film about the survey to help raise awareness and survey completion. The PIS and supporting links and phone number, will also be available for participants to access via the Re:Mission study website (www.remission.study). A prize draw of 12x£50 gift vouchers will be made available to incentivise participation, with a prize draw organised and publicised by the study PPI group (4x prize draws per study year). We anticipate an initial survey response rate of around 30% (~1,500 of the 5,000 anticipated patients) based on an uptake of 33.1% observed in the most recent GP patient survey[55]). NB the participant survey will also be distributed to the additional 11 pilot sites that will operationalised from January 2022, which will expand the available recruitment pool.

*Analysis*: Descriptive and where appropriate inferential statistics will be used to assess any numerical and categorical data in either Excel or SPSS, and free text responses will be synthesised and assessed for emerging themes using Scaled Insights Behavioural Artificial Intelligence software.

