### **Objectives:**

- 1.To undertake ten additional longitudinal interviews, using novel adapted photovoice methodology to explore the lived experience of the LCD programme in patients with co-existing OA, to explore how this may impact on their ability to participate in the programme and whether additional support needs are required.
- 2. To assess IL-6 and hs-CRP in LCD patients with and without OA to determine the impact of the programme on underlying inflammatory pathways.
- 3. Use learning from this study to inform practice and research:
  - a. Develop additional support for LCD patients with MLTC if required.
  - b. Inform the development of personalised approaches to diabetes management

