### A4.1.2 Eligibility criteria

### Inclusion criteria

- (a) Age 18 years or over
- (b) Ability to provide informed consent
- (c) Referral into NHS Low Calorie Diet programme.

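### The sub-study baseline need not precede total diet replacement, so the only pre-programme reference for hs-CRP and IL-6 may be measured on treatment

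*Protocol*

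**What the plan says.** **Sub-study (Protocol Annex 1).** The schedule in A4.1.6 puts consent, eligibility, questionnaires and blood at Visit 1. The only timing rule is a footnote: "As close to commencement of the LCD programme as possible". It does not say before, and it gives no window. Visit 2, in the same table, has a tolerance of four weeks either side.

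Other sections do not close the gap:
- A4.1.3 starts recruitment early: "Potential participants will be provided with a copy of the Participant Information Sheet (PIS) by the Service Provider at their pre-assessment visit". Visit 1 is booked only once the patient has registered interest, when "the central research team will then liaise with the local research site to organise the first study visit". This step is not tied to the TDR start date.
- The eligibility criterion that concerns the programme (A4.1.2) is "Referral into NHS Low Calorie Diet programme". The single exclusion criterion does not mention people already on TDR.

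The sub-study has two measurement points. For the questionnaires, A4.1.5.1 says: "Participants will be asked to complete three additional questionnaires at the baseline and 6 month visits". Blood follows the same two visits. Objective 2 (A2.0) is "To assess IL-6 and hs-CRP in LCD patients with and without OA to determine the impact of the programme on underlying inflammatory pathways". Both cohorts, with and without osteoarthritis (OA), come from programme participants (A4.1.1).

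**Main study (Work package 3, Stage 1).** Here the overlap is explicit: "Baseline survey to be completed between the initial assessment and the first week of the TDR phase".

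**The concern.** A baseline used to measure what a programme does should be taken before the programme begins. With two samples and no untreated group, Visit 1 is the sub-study's only pre-programme reference. If it is drawn on TDR, the Visit 1 to Visit 2 difference no longer spans the whole programme effect, and no later analysis can recover the missing pre-TDR sample.

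Two outputs are exposed:
- the estimated change in hs-CRP and IL-6 that Objective 2 needs;
- the prevalence of systemic inflammation in each cohort (A4.1.8.3), where baseline values would mix people before and during TDR.

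The survey raises the same issue in a milder form. Its wellbeing, EQ-5D, emotional-eating and binge-eating items could be answered in the first TDR week and still be labelled baseline.

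**Working it through.** **Is a late baseline permitted?** The visit schedule, the recruitment route, the inclusion and exclusion criteria and the survey time points were read together. None requires sub-study Visit 1 to precede TDR, and none caps how late it may be. The survey rule caps the overlap at about one week. So a late baseline is permitted in both, without limit in the sub-study.

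**Is there a stated figure to reproduce?** No. A4.1.8.4 says that no formal sample size or power calculation was done. The only arithmetic is 100 + 100 = 200, which agrees.

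**How much could a late Visit 1 matter?** The protocol gives neither the delay nor the time course of any outcome, so both are assumed here.

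Let D be the true change from TDR start to Visit 2, and a the change that has already occurred at Visit 1. Measured change is D − a, so the share lost is a/D. Three time courses are taken, with L weeks of delay:
1. Linear to Visit 2 at week T: loss = L/T. T runs from 18 (end of food reintroduction, 12 + 6 weeks) to 30 (6 months taken as 26 weeks, plus 4). The schedule's 6-month timing and its note tying Visit 2 to the end of food reintroduction do not agree. That must be reconciled separately; here it only sets the range.
2. Linear over the 12 TDR weeks, then flat: loss = L/12.
3. Front-loaded: loss = 1 − exp(−L/τ), with τ assumed to be 8 or 4 weeks.

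| Delay L | Linear to week 30 / week 18 | Linear over TDR, then flat | Front-loaded, τ = 8 / 4 |
|---|---|---|---|
| 1 week | 1/30 = 3.3% / 1/18 = 5.6% | 1/12 = 8.3% | 11.8% / 22.1% |
| 2 weeks | 6.7% / 11.1% | 16.7% | 22.1% / 39.3% |
| 4 weeks | 13.3% / 22.2% | 33.3% | 39.3% / 63.2% |

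These are losses for a participant seen L weeks late. If a proportion p of a cohort is that late, the cohort mean loses p times the figure. The documents give no value for p.

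**Direction.** The table assumes that a and D have the same sign. If a marker or score worsens briefly at the start of TDR and improves later, a has the opposite sign, a/D is negative, and measured change is inflated.

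**Effect on precision (illustration only).** Take 100 per cohort, two-sided 5%, and an assumed between-cohort difference in change of 0.4 SD. Assume also that everyone is equally late. Power ≈ Φ(0.4 × (1 − loss) × √(100/2) − 1.96). This gives 80.7% with no loss, 73.7% at 8.3%, 59.6% at 22.1% and 47.1% at 33.3%.

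**The case against.** The case on the other side has real force.

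- **Permitted is not the same as likely.** Handing out the information sheet at pre-assessment suggests that enrolment before TDR is intended. The documents give no interval from pre-assessment to TDR start or to Visit 1. A reader might infer from the several booking steps that late visits will be common. The text does not support that. This stands.
- **Dilution is not established.** A reader might infer that change is biased towards zero. That needs each outcome to move from the first TDR day in its final direction, which the documents do not show for hs-CRP, IL-6, joint scores, EQ-5D, wellbeing or eating scores. This stands.
- **Bias between cohorts is not shown.** A reader might suppose that people with painful joints attend later, which would bias the OA comparison. No section says so.
- **The survey overlap is small.** It is capped at about one week. The planned survey analysis is descriptive, with inferential statistics where suitable, and names no change estimand. Nor does the survey supply the economic model's baseline BMI, blood pressure and HbA1c, which come from the NHSE minimum dataset (Method C). This stands, and makes the survey a lesser point.
- **The sub-study is exploratory and a statistical analysis plan is promised.** How to analyse late baselines could be left to that plan. When blood is drawn could not, because an analysis plan cannot supply a sample that was never taken.
- **The dates may already be available.** The enrolment log holds the baseline visit date (A4.1.7.3), and linkage to the minimum dataset is planned with permission (A4.1.5.3). The documents do not say that the dataset holds a TDR start date, so this answers the point only in part.
- **Dropping late attenders could cause selection bias.** This stands, and the remedy should keep them.

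**Conclusion.** The point holds in a limited form. The protocol permits the sub-study baseline blood and questionnaires to be taken after TDR has started, with no upper limit, and the main baseline survey up to about one week into TDR. Because Objective 2 depends on two samples without an untreated group, an on-TDR Visit 1 may distort the estimated change in both markers and the baseline prevalence of inflammation.

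Frequency, direction and size are unknown from the documents. If change runs in one direction from TDR start, a one-week delay costs about 3-8% of an affected participant's change under the linear courses and 12-22% under the front-loaded ones. A four-week delay, which the text does not exclude, costs 13-33% under the linear courses and more if front-loaded. All of these rest on assumed delays and time courses. The gap in the timing rule is certain; the amount of bias is not. This is a cheap improvement to make before sub-study recruitment, not evidence that the results will be wrong.

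**What to change.** **A4.1.6.** State that the Visit 1 blood sample and questionnaires are to be taken before the first TDR day. Record the TDR start date for every participant, so that the number of days on TDR at Visit 1 is known. Anyone seen later may still be enrolled. Keep them in the main analysis with adjustment for days on TDR at Visit 1, and run a sensitivity analysis that leaves them out. The rule concerns when measurements are taken and does not touch when the diet starts.

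**Work package 3, Stage 1 (lesser point).** Ask for the baseline survey before TDR starts where possible. Date each response against TDR start, so that first-week responses can be identified in any baseline-to-follow-up comparison. Do not discard them: the anticipated response rate is only around 30%.

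**Cost.** Slightly tighter scheduling of Visit 1, one date field and one sensitivity analysis. Adjustment for days on TDR depends on the form of the model, which is why the sensitivity analysis is needed beside it.

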NHSE have procured two providers per delivery model, four providers in total, who are delivering 12 weeks TDR, followed by six weeks food reintroduction and then 34 weeks weight loss maintenance support, delivered through one of three behaviour change delivery models (one to one, group or digital). Therefore, a robust evaluation of this pilot is required to generate comprehensive insights into the implementation of this programme within routine clinical care. This evaluation will assess associated patient and health care costs; patient experience; inequity in uptake and compliance, and differential effects particularly within high risk groups (Black and South Asian populations, and those of low socio-economic status); the impact and acceptability of different behaviour change models, and the transferability of the model to support wider adoption and policy change.

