### Stage 2: Case study: In-depth patient insights.

Of the participants who express an interest in taking part in this stage of the research (either via the study website, participant survey, or recruited by the service provider), we will undertake maximum variation sampling[56], to gain a range of different perspectives by recruiting people from a variety of backgrounds and experiences from across the three delivery models. This form of sampling is designed to explore multiple facets of a problem and investigate issues holistically[56]. Sampled patients will be invited to take part in a 60 minute one to one telephone interview, undertaken at the end of each phase of the programme (12,18 and 52 weeks), replicating the longitudinal gualitative approach undertaken as part of the Counterbalance study[57] and [name][58]. The purpose of the interviews is to provide in-depth insights into what works, for whom, in what context and why (collecting patient data to assess the mechanism, context and outcomes of the programme). We anticipate recruiting approximately 66 participants - a minimum of six participants who did not start or withdrew from the programme, and at least 30 participants (10 from each delivery model) who start the programme and will be followed up over time. When recruiting six participants who did not start or withdrew from the programme we will aim to sample equally to three groups: those discharged before starting total diet replacement, those discharged during total diet replacement, and those discharged after completing total diet replacement. We will aim to over sample in anticipation of some drop out. The interviews from participants who do not complete the longitudinal interviews will be assessed cross sectionally, additional cross sectional interviews may also be undertaken to explore any key emerging themes in more detail. The interviews will be undertaken using a semistructured interview guide informed by the realist approach, research questions, photovoice materials (where used) and co-production process (to ensure data enriches the NHSE data) and insights from the survey responses. It is anticipated that the interviews will develop insight into patient expectations and experience of the service, and where appropriate: the reason for not engaging, unexpected or unintended outcomes, what was liked most and least about the service, interaction with other services, confidence in implementing the contents, greatest challenges and successes, views on how the service was delivered, impact of the service on the wider family and social networks, resultant lifestyle changes and achievements, and further explore the context such as the impact of cultural differences, the effect of family and social networks and / or the place of food in the daily lives of participants. The interviews will be supported by our socio-demographically diverse PPI group, who will also be trained in undertaking interviews, so participants can opt to be interviewed by a trained PPI member alongside the study researcher, in recognition of the benefits of having community members as researchers. Prior to each interview participants will also be invited to undertake a 24hr dietary review (using myfood24), either with the researcher after completing the interview or independently beforehand, to track more detailed dietary changes that may occur during the programme. Gift vouchers will be offered to incentivise participation, and translators will be made available for any participants who wish to undertake an interview in another language.

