### Method (A) Intervention delivery cost analysis (RQ9)

The incremental cost of delivering the intervention when compared to routine care will be assessed for the three different delivery models during the three distinct delivery stages (weeks 1-12, 13-18 and 19-52) of the programme. A bottom-up, micro-costing approach will be used following best practice guidance [66-68].

Data collection will take place as fully integrated components of the semi-structured interviews, focus groups and electronic questionnaire (STAR-LITE) conducted with NHS staff and providers (see WP2 of the main Re:Mission study protocol). In addition to the existing cost questions in STAR-LITE that elicit a free text response, further questions will be designed to elicit details about specific resources used and (where not adequately captured in national databases) their unit costs. Unit costs elicited in this study will be cross-checked with appropriate external sources (e.g. sellers and suppliers of relevant products, national healthcare databases [69, 70] such as PSSRU - Personal Social Services Research Unit data) and published cost analyses of comparable interventions.

The specific resource items to be included in the questionnaire are based on items identified in the DiRECT trial cost analysis[17], other published cost analyses of comparable interventions[71] and through discussions with NHSE. They include (but are not limited to) components of intervention materials, practitioner and patient meetings, and extra patient consultations.

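### Annex 1 sub-study: the Visit 2 window (6 months ± 4 weeks) does not contain week 18, the end of food re-introduction with which the visit is meant to coincide

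*Protocol*

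**What the plan says.** **Sub-study schedule.** The table in Annex 1, A4.1.6 has one follow-up visit, Visit 2, at 6 months with a window of ± 4 weeks. Two footnotes follow. The asterisk belongs to Visit 1: "As close to commencement of the LCD programme as possible". The caret footnote reads: "To coincide with completion of the food re-introduction phase". In the text read from the PDF the caret is not attached to any column heading, and the marker may simply have been lost. Visit 2 is the only visit it can describe, because Visit 1 carries the asterisk and the pre-baseline column precedes the programme.

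**Other places that fix the follow-up at 6 months.** A4.1.5.1 states: "Participants will be asked to complete three additional questionnaires at the baseline and 6 month visits". A4.2 (Work Package B) sets the last sub-study interview at 6 instead of 12 months, so that data collection fits the end of the funded evaluation.

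**When re-introduction ends.** The Background describes the programme as "12 weeks TDR, followed by six weeks food reintroduction and then 34 weeks weight loss maintenance support", and the rationale of Work package 4 repeats these lengths. Method (A) gives the delivery stages as "weeks 1-12, 13-18 and 19-52". The main-study interviews are "undertaken at the end of each phase of the programme (12,18 and 52 weeks".

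**What depends on Visit 2.** Sub-study Objective 2 is: "To assess IL-6 and hs-CRP in LCD patients with and without OA to determine the impact of the programme on underlying inflammatory pathways". A4.1.5.2 ties the blood to the visits: "A maximum of 9 mls of blood will be taken at each study visit to enable measurement of inflammatory biomarkers". With two visits there are two samples per participant, and Visit 2 supplies the only one after baseline.

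**The concern.** A schedule and its own footnote should name the same moment. Here one names a calendar time and the other a programme event, and by the Protocol's phase lengths these lie about two months apart.

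The biological context differs between them. At week 18 a participant has just finished the diet phases. Between weeks 22 and 30 the same participant is in weight-maintenance support. A biomarker level at one time does not answer quite the same question as a level at the other. Objective 2 asks about the effect of the programme on inflammatory markers and rests on this single follow-up sample, so its meaning depends on which instruction is followed.

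This cannot be left to the analysis plan. The protocol fixes visit timing, and an analysis can describe when blood was drawn but cannot supply a sample that was not taken at the intended time.

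**Working it through.** This is calendar arithmetic; no power or sample-size formula applies.

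**Inputs**
- Phase lengths: 12, 6 and 34 weeks (Background; Work package 4 rationale).
- Phase boundaries: weeks 1–12, 13–18 and 19–52 (Method A); phase ends at 12, 18 and 52 weeks (Work package 3, Stage 2).
- Visit 2: 6 months ± 4 weeks (A4.1.6).

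**Step 1. End of re-introduction.** 12 + 6 = 18 weeks. As a check, 12 + 6 + 34 = 52 weeks, which agrees with the stated boundaries.

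**Step 2. Visit 2 window.** The Protocol does not convert months to weeks, so three readings are tried. Window = target ± 4; shortfall = lower limit − 18.

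| Reading of 6 months | Target (weeks) | Window (weeks) | Week 18 inside? | Weeks before window opens | Weeks before target |
|---|---|---|---|---|---|
| Calendar: 6 × 365.25 / 12 / 7 | 26.09 | 22.09–30.09 | No | 4.09 | 8.09 |
| Half a 52-week year | 26 | 22–30 | No | 4 | 8 |
| Four-week months | 24 | 20–28 | No | 2 | 6 |

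Week 18 is outside the window on every reading.

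**Step 3. Where an in-window visit falls.** With the 22–30 window, 22 − 18 = 4 and 30 − 18 = 12, so the visit is 4 to 12 weeks into maintenance. With four-week months it is 2 to 10 weeks.

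**Step 4. Does a different time origin rescue it?** The Protocol does not say whether the 6 months run from Visit 1 or from the first day of total diet replacement (TDR). Suppose they run from Visit 1, and Visit 1 precedes TDR by L weeks. Re-introduction then ends at 18 + L weeks from Visit 1.
- 22–30 window: 18 + L ≥ 22 needs L ≥ 4.
- Calendar months: 18 + L ≥ 22.09 needs L ≥ 4.09, that is 5 whole weeks.
- Four-week months: 18 + L ≥ 20 needs L ≥ 2.

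A planned gap of 4 weeks or more does not fit the instruction to hold Visit 1 as near the programme start as possible. Only both lenient assumptions together (four-week months and counting from an early Visit 1) bring the required gap down to 2 weeks, and the Protocol states neither.

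**The case against.** The strongest reply is that this is one stray footnote. Six months appears in the Visit 2 column heading and in A4.1.5.1, and A4.2 uses it for the last interview with a reason given. Against that stands a single footnote whose marker is not visible on any column. A sensible site would probably book 6 months. The sub-study is also declared exploratory (A4.1.8.2), has no power calculation (A4.1.8.4) and plans mainly descriptive analyses (A4.1.8.3).

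Much of this stands. It limits the severity and suggests that the repair may be no more than a deletion. It does not remove the contradiction: the footnote is current text, nothing marks it as an error, and it governs the only follow-up sample.

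A reader might go on to infer more than the documents support:
- **Follow-up restricted to people who complete the phase.** No section says so. A4.1.5.1 asks participants for questionnaires without restriction, the 6-month anchor gives programme leavers a date, and A4.1.4.1 and A4.1.4.2 deal with withdrawal from the study, not from the programme.
- **Baseline blood taken during TDR, shrinking the measured change.** Visit 1 has no latest date, so this is possible. But A4.1.3 starts recruitment at the pre-assessment visit, no section plans a late baseline, and A4.1.8.3 defines no change score. It is a separate risk.
- **Samples spread over 12 weeks, from week 18 to week 30.** This assumes that sites split between the two anchors, which nothing shows. The stated window already allows 8 weeks.

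**Conclusion.** The contradiction holds. For a participant on the standard timetable, the end of food re-introduction is about 4 weeks before the Visit 2 window opens and about 8 weeks before its target; with four-week months the gaps are 2 and 6 weeks. Either timing can be followed, but not both.

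This rests on three assumptions: the caret footnote refers to Visit 2; the participant moves through the phases at the stated lengths; and Visit 1 does not precede TDR by about 4 weeks or more (2 weeks if months are four weeks long).

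The consequence is ambiguity about what the follow-up hs-CRP, IL-6 and questionnaire scores represent, in both the osteoarthritis and the comparison cohort. It would be too strong to say that the follow-up has no usable meaning or that a bias has been shown. The effect is confined to an exploratory sub-study and leaves the main evaluation untouched. It is wrong as written and should be fixed.

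**What to change.** Choose one anchor for Visit 2 and remove the other. The Protocol does not settle which was intended, so the choice is the sponsor's:
- keep 6 months ± 4 weeks and delete the caret footnote; or
- define Visit 2 at the end of re-introduction, with a window that contains week 18, and drop the 6-month label.

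In either case, state the day from which time is counted (Visit 1 or the first day of TDR), and attach any remaining footnote visibly to its column. Then make A4.1.5.1, A4.1.6 and A4.2 agree. If Visit 2 moves to the end of re-introduction, A4.2 needs a deliberate decision, because its last interview is separately set at 6 months and would otherwise no longer fall at the time of the visit.

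The cost is wording in the schedule, the two related sections and the case report form. No visit or sample is added. Annex 1 still shows approval as pending, so the correction can be made before the first sub-study participant is enrolled.
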